1.0 Study Summary

| Study Title | Laryngeal mask airway versus endotracheal intubation for | | |
|-------------------------|---|--|--|
| | laparoscopic inguinal hernia repair | | |
| Study Design | Prospective Randomized | | |
| Primary Objective | Evaluate the effectiveness of LMA versus ETT for patients | | |
| | undergoing laparoscopic inguinal hernia repair by | | |
| | measuring SpO2 at 3 standardized timepoints | | |
| Secondary Objective(s) | 1. Evaluate EtCO2 in both groups at three standardized | | |
| | timepoints | | |
| | 2. Evaluate peak airway pressures in both groups at three | | |
| | standardized timepoints | | |
| | 3. Documentation of laryngospasm occurrence in both | | |
| | groups | | |
| Study Population | 12 mo- 8 yo patients undergoing laparoscopic inguinal | | |
| | hernia repair at CMH or CMK | | |
| Study Duration for | Single visit during which inguinal hernia repair is performed | | |
| Individual Participants | | | |
| Study Specific | LAR – Legally Authorized Representative | | |
| Abbreviations/ | LMA – Laryngeal Mask Airway | | |
| Definitions | ETT- Endotracheal tube | | |

2.0 Objectives*

2.1 Purpose, specific aims or objectives: Describe the purpose, specific aims, or objectives. If more than one objective be sure to list separately.

This study aims to evaluate the effectiveness during general anesthesia of laryngeal mask airway versus endotracheal tube for laparoscopic inguinal hernia repair.

2.2 Hypothesis: Use of laryngeal mask airway is not inferior to the use of endotracheal intubation for patients undergoing laparoscopic inguinal hernia repair.

3.0 Background*

3.1 Describe the relevant prior experience and gaps in current knowledge.

Children undergoing laparoscopic inguinal hernia repair typically received general anesthesia with endotracheal intubation. There are limited studies looking at the use of laryngeal mask airway for short laparoscopic procedures in pediatric patients.^{1,2}

3.2 Describe any relevant preliminary data.

There are limited pediatric literature evaluating the use of laryngeal mask airway for laparoscopic procedures compared with traditional endotracheal intubation.¹ This study aims to add to this literature in providing information comparing the two techniques.

3.3 Provide the scientific or scholarly background for, rationale for, and significance of the research based on the existing literature and how it will add to existing knowledge.

The rationale for this study is to show that general anesthesia with laryngeal mask airway is an effective and non-inferior technique compared with general anesthesia with endotracheal intubation in pediatric patients undergoing laparoscopic inguinal hernia repair and may offer benefits in terms of efficiency of care and respiratory complications.

References

4.0 Study Endpoints

4.1 Describe the primary and secondary study endpoints.

The primary endpoint of this study will be SpO2 measured at 3 standardized timepoints.

Secondary endpoints will include:

- SpO2 less than 90%
- End tidal CO2 measurement at 3 standardized timepoints
- Peak airway pressures measured at 3 standardized timepoints

• Occurrence of laryngospasm

4.2

The safety endpoint would be conversion to general endotracheal anesthesia.

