5.2 Table of Events: *n/a*

6.0 Study Interventions*

6.1 Description: In this study, patients will undergo general anesthesia for laparoscopic inguinal hernia repair. The study intervention being evaluated is the placement of laryngeal mask airway instead of endotracheal intubation. Both LMA and endotracheal intubation are standard care anesthesia practices at CMH for various procedures, including sometimes laparoscopic hernia repair. This study will randomize the airway, but all other anesthesia drugs and procedures remain the same in both groups.

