28.0 Statistical Analysis*

28.1 The data analysis will be a simple calculation of demographics and incidence of complications. Comparison between groups will be completed using chi square for categorical variables and t-test for continuous variables. Statistical significance will be set at p-value <0.05

We determined the targeted sample size of 50 patients using a power calculation using the following parameters: 90% power, 2.5% Type I error rate, non-inferiority limit of 5% point of SP02, no difference between treatments, and standard deviations of 1, 2, 5, and 10.

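### Primary SpO2 analysis does not test the non-inferiority hypothesis: t-tests at p<0.05 with no use of the 5-point limit, three unnamed timepoints and no rule for combining them

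*Combined protocol and SAP*

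**What the plan says.** - **Hypothesis (Section 2.2):** "Use of laryngeal mask airway is not inferior to the use of endotracheal intubation".
- **Primary endpoint (Section 4.1):** "The primary endpoint of this study will be SpO2 measured at 3 standardized timepoints". The objective in Section 1.0 uses the same phrase, "measuring SpO2 at 3 standardized timepoints". No section names the timepoints, and the table of events in Section 5.2 is marked not applicable.
- **Analysis (Section 28.1):** "Comparison between groups will be completed using chi square for categorical variables and t-test for continuous variables", then "Statistical significance will be set at p-value <0.05".
- **Sample size (Section 28.1):** 50 patients, based on "90% power, 2.5% Type I error rate, non-inferiority limit of 5% point of SP02", no true difference, and SDs of 1, 2, 5 and 10. The SD on which 50 rests is not identified, and the 2.5% is not described as one- or two-sided. Section 8.1 gives 25 per group.

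The margin and the 2.5% error rate appear nowhere else. There is no confidence-interval criterion, shifted null hypothesis, primary timepoint, summary measure, repeated-measures model, combining rule or multiplicity adjustment.

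**The concern.** A standard t-test takes zero difference as its null hypothesis. Non-inferiority takes a deficit of 5 points or more as its null. The two can disagree in either direction: a small deficit well inside the limit can be significant, and a deficit at the limit can be non-significant when the data are noisy. Neither p-value answers the question in Section 2.2.

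Tying the test to the limit would still leave three results for one hypothesis. Success at any timepoint inflates the error rate, success at all three costs power at larger SDs, and a per-child mean can hide a drop at one timepoint. Sections 26.2 and 29.1 say the data are taken from the medical record after the procedure. Both the readings that count and the combining rule could therefore be settled once results are visible.

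**Working it through.** **Inputs from the documents:** 25 per arm (8.1); margin 5 points, true difference 0, 90% power, 2.5% error, SDs 1, 2, 5 and 10 (28.1). **Assumed:** all 25 per arm analysed, normal data, and correlation rho of 0 to 0.9 between timepoints. The documents give no correlation.

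**1. The plan's own figure.** For one comparison, n per arm = 2(z₁₋α + z₀.₉₀)²(SD/5)².
- SD 5, α = 0.025 one-sided: 2(1.960 + 1.282)² = 21.01, so 22 per arm and 44 in total (46 by noncentral t).
- SD 5, α = 0.0125 per side: 2(2.241 + 1.282)² = 24.8, so 25 per arm and 50 in total (54 by noncentral t).
- SD 10, α = 0.025 one-sided: 85 per arm and 170 in total.

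The stated 50 is matched by a single comparison at SD 5 with the 2.5% read as two-sided. The calculation contains no term for three timepoints.

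**2. Why the two tests disagree.** The 95% interval half-width is t₀.₉₇₅,₄₈ × SD × √(2/25) = 2.011 × 0.2828 × SD. This is 1.14 at SD 2 and 5.69 at SD 10.
- Observed difference -2, SD 2: interval -3.14 to -0.86. This is significant, yet it clears -5.
- Observed difference -5, SD 10: interval -10.69 to 0.69. This is non-significant, yet it fails -5.

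**3. Zero-difference t-tests at each timepoint (simulated, two-sided 0.05).**

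| True state at all three timepoints | Result | rho 0 | rho 0.5 | rho 0.9 |
|---|---|---|---|---|
| -2, SD 2 | at least one significant | 1.000 | 0.993 | 0.965 |
| -5, SD 10 | none significant | 0.206 | 0.337 | 0.481 |
| -5, SD 5 | none significant | 0.000 | 0.008 | 0.034 |
| -5, SD 2 | none significant | 0.000 | 0.000 | 0.000 |
| 0 | at least one significant | 0.142 | 0.126 | 0.082 |

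In the first row, requiring the lower 95% limit to exceed -5 at all three timepoints claims non-inferiority in 0.998 to 0.999 of trials.

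**4. Effect of the combining rule once the t-test is shifted by the margin.** The plan does not state this shift. Pairs are one-sided 2.5% / 1.25% per side.

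| Quantity | rho 0 | rho 0.5 | rho 0.9 |
|---|---|---|---|
| Any-of-three, true -5 at all three: false claim | 0.073 / 0.037 | 0.063 / 0.032 | 0.042 / 0.022 |
| All-three power, SD 4 | 0.973 / 0.942 | 0.976 / 0.949 | 0.985 / 0.967 |
| All-three power, SD 4.5 | 0.912 / 0.838 | 0.926 / 0.865 | 0.951 / 0.909 |
| All-three power, SD 5 | 0.815 / 0.695 | 0.844 / 0.750 | 0.895 / 0.827 |
| Per-child mean power, SD 5 | 1.000 / 1.000 | 0.989 / 0.976 | 0.947 / 0.906 |
| Per-child mean, true -5 at one timepoint only, SD 5: claims non-inferiority | 0.980 / 0.961 | 0.807 / 0.716 | 0.667 / 0.555 |

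One comparison at SD 5 has power 0.934 / 0.885, and at SD 10 it has 0.410 / 0.302. With a deficit at one timepoint only, the all-three rule makes a false claim in 0.022 to 0.026 / 0.010 to 0.014 of trials.

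**The case against.** The strongest reply is that Section 28.1 does not say the t-test's null is zero. The margin is in the same section, the hypothesis is non-inferiority, and a two-sided 0.05 test corresponds to a 95% interval whose lower limit could be compared with -5. On that view the plan is under-specified rather than wrong. This stands in part: a reader could supply the margin. But an unqualified t-test with a significance threshold means a test of zero difference, and supplying the margin would still leave three results and no rule.

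Other points limit the size of the concern.
- Any-of-three success is not proposed anywhere in the plan, so its error rate is a risk left open, not a planned error.
- Of the four listed SDs, only SD 5 shows a power loss due mainly to the combining rule. At SD 1 or 2, all-three power exceeds 99%. At SD 10 even one comparison is underpowered, which is a sample-size problem.
- The non-significance error is large only at SD 10.
- A significant test under a true 2-point deficit is a correct detection of a difference. It misleads only if read as failed non-inferiority, and the plan gives no other reading.
- SpO2 cannot exceed 100%, so normal data with an SD of 5 or 10 are doubtful and those figures are approximate.

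None of this supplies the missing decision rule.

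**Conclusion.** The concern holds. The analysis in Section 28.1, taken literally, does not test the hypothesis in Section 2.2, and no section says how the three timepoints yield one conclusion. The mismatch of test and hypothesis matters even at small SDs, where differences well inside the limit become significant (96% to 100% of trials for a 2-point deficit at SD 2). The opposite error, a non-significant result at a true 5-point deficit, is 21% to 48% at SD 10 and under 4% at SD 5. The choice of combining rule moves the one-sided error from 2.5% to between 4.2% and 7.3% (any-of-three). At SD 5 it moves power from 93% to between 81% and 89% (all-three, one-sided). The power loss is confined to SDs above about 4 to 4.5.

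These figures rest on 25 analysed per arm, normality and the assumed correlations. They do not show that 50 patients is too few. The change should be made before the data are examined.

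**What to change.** In Section 4.1, name the three timepoints before data extraction.

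In Section 28.1, replace the p<0.05 difference test for the primary endpoint with the lower confidence limit for LMA minus ETT compared with -5. Use a 95% two-sided interval if the 2.5% is one-sided, or a 97.5% interval if it is two-sided, and state which. Then pre-specify one rule:

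- **(a)** The limit exceeds -5 at all three timepoints. No alpha adjustment is needed. Restate power as conditional on the SD, the correlation and the sidedness.
- **(b)** One comparison of the per-child mean of the three readings, with each timepoint reported with its confidence interval as supportive.

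Do not allow success at any single timepoint without adjustment.

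**Cost:** wording only, with no new data. No extra patients are needed if the power under (a) is accepted as it falls. At SD 5 that is 81% to 89% one-sided, or 69% to 83% at 1.25% per side. Holding 90% under (a) at SD 5 with uncorrelated timepoints needs per-comparison power of 0.90^(1/3) = 0.965. By noncentral t that is 30 per arm (60 in total) one-sided, or 35 per arm (70 in total) at 1.25% per side. The 20 extra patients in Section 8.1 are already assigned to screening failures and withdrawals. Option (b) keeps power but can hide a drop at one timepoint: with a 5-point deficit at one timepoint only, it claims non-inferiority in 67% to 98% of trials at SD 5 and about 100% at SD 2 (one-sided 2.5%). At SD 4 or below, (a) already has at least 94% power, so (b) gains little there.

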5.0 Study Design*

5.1 Study Design: This will be a single institution prospective randomized study. Patients preparing for laparoscopic inguinal hernia repair (and meeting other inclusion criteria), whose parent or LAR provides permission to participate in the study, will be randomized to receive either general anesthesia with laryngeal mask airway placement or endotracheal tube placement and their data will be recorded. Patients who choose not to participate will be given either standard treatment per their assigned anesthesiologist.

5.2 Table of Events: *n/a*

6.0 Study Interventions*

6.1 Description: In this study, patients will undergo general anesthesia for laparoscopic inguinal hernia repair. The study intervention being evaluated is the placement of laryngeal mask airway instead of endotracheal intubation. Both LMA and endotracheal intubation are standard care anesthesia practices at CMH for various procedures, including sometimes laparoscopic hernia repair. This study will randomize the airway, but all other anesthesia drugs and procedures remain the same in both groups.

6.2 Behavioral Intervention: N/A

6.3 Drugs, Biologics, or Devices: No experimental drugs or devices will be used in this study.

PARTICIPANT MANAGEMENT

7.0 Inclusion and Exclusion Criteria*

- 7.1 Eligibility Criteria:
 - 1. Inclusion Criteria
 - 1. Patients undergoing laparoscopic inguinal hernia repair.
 - 2. Ages 12 months to 8 years of age

- American Society of Anesthesiologists Physical Status Classification ASA 1 or 2
 - 1. ASA 1- A normal, healthy patient
 - 2. ASA 2- A patient with mild systemic disease
- 4. Elective with appropriate NPO status
- 5. English speakers

2. Exclusion Criteria

- 1. Patients with current gastroesophageal reflux
- 2. Obesity (CDC >= 95^{th} %ile)
- 3. Contraindications to study protocol medications

7.2 Equitable Selection: Inclusion/exclusion criteria should be both fair and appropriate to the research question. If the study involves inclusion/exclusion criteria based on demographic characteristics such as sex, race/ethnicity, language, provide rationale for the criteria. For example, if excluding non-English speaking participants, provide rationale for why it is not possible to include non-English speaking participants.

Due to the limited sample size of patients enrolled, there is little to no anticipation of enrolling a non-English speaking patient. If a non-English speaking patient arises, the proper modifications will be put in place to present patient with translated consent forms and protocol, if need be.

7.3 Vulnerable Populations: Check any vulnerable populations that are being targeted for enrollment into the study: (Members of the following populations may not be included as participants in the research unless selected here.)

Children/Minors (under 7 years of age)

Children/Minors (7-17 years of age)

Neonates (infants less than 30 days old)

Reonates of Uncertain Viability (infants)

less than 30 days old)

Non-Viable Neonates (infants less than

30 days old)

□ Wards of the State

Fetuses

Pregnant Women

□ Adults with impaired decision-making capacity

CM Employees
 CM Students/Residents/ Fellows
 Economically or Educationally
 Disadvantaged Persons

8.0 Local Number of Participants

8.1 Indicate the total number of participants or charts to be enrolled locally as well as the accrual goal. If the study includes multiple groups or cohorts, be sure to describe the number of participants required for each cohort. If one of the groups includes a chart review, each chart is considered a participant and needs to be reflected in the numbers below.

□ Prisoners

| | Group 1 | Group 2 | Totals |
|--|---------|-----------------|--------|
| | | (if applicable) | |
| Enrollment Goal: Number of participants to be enrolled = the number of participants to be consented or to be screened for chart reviews. | 25* | 25* | 50* |

*The total enrollment goal will remain 50 patients, but an additional 20 patients will be enrolled to accommodate screening failures and withdrawals.

9.0 Identification and Recruitment of Potential Participants*

9.1 Identification of Potential Participants:

How will participants be identified? (Check all that apply)

 $extsf{ }$ Chart reviews

□ By their treating physician who will then provide the study team's contact information to the potential participant/family

□ By their treating physician who will obtain patient/family permission to share contact information with the study team

□ Self-refer in response to IRB approved advertisements or websites

□ Through Cerner or other CM sources (e.g. databases, billing records, pathology reports, admission logs, etc.) May involve access of records by individuals not involved in the patient's care.

 \Box List of candidates provided through the Data Report Request Form

SHORT TITLE:

□ Registry of individuals interested in research opportunities

□ Past participant list

□ Participants will roll-over from another research study: Study #

⊠ Other: By treating provider, such as anesthesiologist or APRN, who is also a study team member, and who will discuss study with parent(s) and obtain informed consent (parental permission).

9.2 Pre-Screening prior to HIPAA Authorization

Will any of the identification methods checked above involve access to Protected Health Information (PHI) prior to obtaining HIPAA Authorization?

🗆 Yes

🛛 No

• If yes, a "Partial Waiver of HIPAA Authorization" is required. Be sure to make this selection in the "HIPAA & Confidentiality" section below and complete Addendum E: Waiver/Alteration of HIPAA Authorization

9.3 Recruitment of Potential Participants:

Parents of eligible patients presenting for laparoscopic inguinal hernia repair and being treated by a member of the study team, will be presented with information about the study prior to beginning anesthesia when completing the preoperative evaluation. Electronic medical records will be accessed to deem patients eligible. Parents will be given time to ask questions and consider whether to enroll their child in this study.

10.0 Surveys and Psychometric Testing:

N/A

11.0 Additional Study Activities

- Additional study activities will include secondary data use recording data from the medical record after the procedure is complete.
- **11.1** Blood and Other Specimen Collection:

1. N/A- no blood or other specimens will be collected for this study.

12.0 Follow-up

• N/A- no follow up is planned as part of this study.

13.0 Genetic Analysis Information

N/A- no genetic analysis is planned as part of this study.

14.0 Sharing of Results with Participants

14.1 There are no plans to share results of the study with the participants, as their procedures will be complete before data is analyzed and results are available.

15.0 Risks to Participants*

15.1

- This study involves no greater than minimal risk to participants, as the risks are similar to those that patients would encounter undergoing general anesthesia for a procedure. Both LMA and ETT are commonly used standard anesthesia practices for various procedures.
- There is also minimal risk to privacy associated with the chart review aspect of this study. All data will be stored securely on the CMH network and in REDCap. Only IRB-approved study team members will have access to the data.
- **15.2** This study involves no greater than minimal risk.
- **15.3** N/A
- **15.4** N/A
- **15.5** N/A

16.0 Potential Benefits*

16.1 Potential benefits include:

Potentially decreased time in operating room for LMA group. Potential benefit of avoiding ETT and possible decreased risk of respiratory complications. Possible

decrease in laryngospasm, bronchospasm, and postoperative respiratory complications.

17.0 Investigator Assessment of Risk/Benefits Ratio*

17.1 Please provide an assessment of risk and benefits in the table below. Note, the IRB makes the final determination based upon responses in the two preceding sections.

| Select as applicable: | Pediatric Risk Category: | |
|-----------------------|-------------------------------|--|
| \boxtimes | Category 1 | Research not involving greater than minimal risk |
| | | (45 CFR §46.404 and 21 CFR §50.51) |
| | Category 2 | Research involving greater than minimal risk but |
| | | presenting the prospect of direct benefit to the |
| | | individual participants. (45 CFR §46.405 and 21 CFR |
| | | §50.52) |
| | Category 3 | Research involving greater than minimal risk and no |
| | | prospect of direct benefit to individual participants, |
| | | but |
| | | likely to yield generalizable knowledge about the |
| | | participant's disorder or condition. |
| | | (45 CFR §46.406 and 21 CFR §50.53) |
| | Category 4 | Research not otherwise approvable which presents |
| | | an opportunity to understand, prevent, or alleviate a |
| | | serious problem affecting the health or welfare of |
| | | children. (45 CFR §46.407 and 21 CFR §50.54) |
| Select if applicable: | Adult Risk Category: | |
| | Not Greater than Minimal Risk | |
| | Greater than Minimal Risk | |

18.0 Payment, Reimbursement and Tangible Property provided to participants*

Is payment, reimbursement, or tangible property part of the study?

19.0 Compensation for Research-Related Injury

19.1 This study is internally funded, involves no more than minimal risk and there is no planned compensation available in the event of research related injury.

20.0 Economic Burden to Participants

20.1 There are no costs to patients directly related to participation in this study. Patients or their insurance will be billed for anesthesia received for their procedure whether enrolled in this study or not.

21.0 Parental Permission and Adult Consent Process*

21.1 Indicate below all methods of Permission/Consent that will be used in this study.

- If the study includes **multiple study groups**, be sure to indicate which method is being used with each group.
- If requesting a Waiver of Documentation, a complete Waiver, or an Alteration, complete the required addendum at the end of this document.

Written Informed Permission/Consent

Written informed permission of parent/LAR for pediatric participants

Study group(s) to which this method applies: Parent/LAR of participant

□ Written informed consent of adult participants

Study group(s) to which this method applies:

\Box Written informed consent of participants turning 18

This includes the continued access to and use of their PHI by the study team.

Study group(s) to which this method applies:

Waiver or Alteration of Permission/Consent

Parent/LAR permission/adult consent will **NOT** be obtained, or an alteration to an element(s) of consent.

Must complete Addendum B: Waiver of Permission/Assent/Consent

□ Waiver/Alteration of permission of parent/LAR for pediatric participants

Study group(s) to which this method applies:

□ Waiver/Alteration of consent of adult participants

Study group(s) to which this method applies:

Waiver/Alteration of consent of participants turning 18

Study group(s) to which this method applies:

21.2 Permission/Consent/Consent at 18 Discussion: If selected options for "Written" or "Waiver of Documentation" above, describe below how the informed permission/consent discussion will be conducted. Describe:

- Where and when the discussion will take place. The informed permission discussion will take place at CMH on the day of surgery. A study team member, likely an Anesthesia APRN, will meet with the family prior to the child starting anesthesia, and will discuss the study with the parents.
- To reduce coercion and undue influence, parents will be informed that their decision whether to participate in this study will not impact their child's care at CMH. If they choose not to participate, their child will receive standard care general anesthesia for their hernia repair.
- eConsent will be used as an option for obtaining consent, which could reduce the possibility of clerical errors on consent forms while also helping to provide access to consent records between study teams in both Surgery and Anesthesia departments involved in this study
- Study staff will try to meet with parents early enough before the procedure to allow time for parents to ask questions and consider enrollment decisions before needing to proceed with anesthesia and surgery procedures.
- Study staff will ensure that parents understand what the study involves by incorporating techniques such as the teach-back method (asking parents to explain their understanding of the study before signing the consent form).
- N/A- telephone permission/consent will not be used.

21.3 Documentation of Permission/Consent/Consent at 18: If selected "Written" options above, explain how informed permission will be documented. Describe:

• Informed permission will be documented in the medical record according to CM Research Policy "10.04 Obtaining Permission/ Assent/ Consent" and "Research Documentation in the Electronic Health Record."

21.4 Identification of participants turning 18: We are requesting a Waiver of Consent at 18 (see Addendum B). This study will only enroll patients up to age 8. We do not anticipate that this study will continue for 10 years or more, until the time the oldest potential participants could turn 18. Although the study will be closed by then, we are requesting a Waiver of Consent at age 18 to be able to

continue to retain data from this study in our Department of Surgery Data Repository (DSDR) after participants turn 18.

